### **Statistical Analysis Plan**

The analysis will begin by describing the baseline demographic and clinical characteristics of the overall population and then stratified by treatment arm to compare those who receive CSP and those who receive standard care. For discrete variables, proportions will be generated, and a chi-square test will be used to test for differences between the proportions. For continuous characteristics, means (medians) and standard deviations (interquartile ranges) will be calculated, and t-tests (Wilcoxon) will be used to compare the means (distributions) between treatment arms.

**Eligibility, Enrollment, and Participant Accrual:** The feasibility of enrollment will be evaluated by determining 1) the proportion of eligible patients that can be randomized, 2) the proportion of eligible patients who are enrolled in the trial, 3) proportion of enrolled patients which adherence to the study protocol, and 4) proportion of enrolled patients who complete study follow-up. These proportions will be estimated directly as the observed ratio of numbers of patients, and 95% confidence intervals will be calculated to understand the likely range of values for a larger study with a comparable research protocol and population. The reasons why patients are not enrolled including frequencies of individual exclusions and the proportion of patients declining participation or not able to be randomized will be described. Rate of participants' accrual per month with 95% C.I. will be calculated.

**Analysis for Clinical Outcomes:** The principal secondary clinical outcome for the trial will be 6-month Extended Glasgow Outcome Scale (GOS-E). The null and alternative hypothesis of the study are

H0: There is no difference in the distribution of the GOS-E scores by treatment group  
H1: There is a difference in the distribution of the GOS-E scores by treatment group

A two-sided Chi-square test will be used to compare the distribution of the GOS-E between the treatment arms. An ordinal polytomous regression model will then be used to assess the independent impact of CSP on GOS-E after controlling for potential confounding effects of baseline characteristics which reveal imbalance between treatment groups. The analytic approach for the secondary trial outcomes will vary based on the type of outcome. For binary outcomes, a two-sided Chi-square test for proportions will be used to compare the proportions between those receiving and not receiving CSP. A logistics regression model will then be used to assess the independent impact of CSP on the secondary trial outcomes while adjusting for baseline GCS. For time-to-event outcomes (e.g., time to death), Kaplan-Meier curves will be generated for each treatment group and a log-rank test will be used to compare the distribution of the cumulative proportion. A Cox-proportional hazards regression model will be used to assess the independent impact of CSP on time to death after controlling for baseline GCS. For continuous outcomes a two-sided t-test for means will be used to compare the means between those receiving and not receiving CSP. An analysis of covariance model will be used to assess the independent effect of CSP. after controlling for baseline GCS .

Analyses to test for the homogeneity of the treatment effect will be carried out for the pre-defined subgroups. Regression models appropriate for the outcome variable (e.g., logistic regression for binary outcome variables) will stratified by the pre-defined subgroups. Estimate of the treatment effect (odds ratio) and 95% confidence interval will be generated for each model and displayed on a forest plot.

Secondary analyses will be conducted to assess the impact of age of the CSP on outcomes. These analyses will be carried out among those who are randomly assigned to the CSP group and the impact of the age of the CSP on outcomes will be evaluated. Since the sample will not be randomly assigned, it will be important to adjust for potential confounding effects. A propensity score will be generated as an indicator of the age of the CSP ( $\leq 7$  days vs.  $> 7$  days). Multivariable regression models will be used to assess the independent relationship of age of the CSP on outcome. The model type will vary based on the outcome (e.g., logistic regression for binary variables). Each model will include a fixed main effect for the indicator of the age of the CSP as well as an inverse probability weight for the propensity of getting CSP  $\leq 7$  days of age.

**Sample Size Justification and Power Analysis (n=100):** For the enrollment, adherence and event rates needed for planning and feasibility analyses, we calculated the two-sided 95% CI for proportions ranging from 0.70 to 0.90. For example, a sample size of 100 produces a two-sided 95% CI of 0.82 to 0.95 when the sample proportion is 0.90. When the sample proportion is .70, the two-sided CI is 0.60 to 0.82. These confidence intervals are then repeated within the treatment arm.

Sample Size	Width	Proportion (P)	Lower Limit	Upper Limit
Full Sample				
100	0.19	0.700	0.60	0.82
100	0.17	0.800	0.71	0.87
100	0.13	0.900	0.82	0.95

One Treatment Arm				
50	0.27	0.700	0.55	0.82
50	0.24	0.800	0.66	0.90
50	0.19	0.900	0.78	0.97

For the principle secondary clinical outcome of the GOSE, based on a 2x8 (treatment x GOSE) there is 80% power to detect an effect size of 0.3788, assuming a type I error rate of 0.05, a two-sided alternative hypothesis, 7 degrees of freedom, and a sample size of 50 participants per treatment group.

**Randomization of Ineligible Participants:** It is anticipated that there will be a small proportion of patients enrolled who receive CSPs or standard care that in retrospect will not have met the entry criteria and are thus ineligible. In this circumstance, patients will be analyzed according to the group to which they were randomized. Subgroup analyses based on eligibility criteria will be performed if the number of patients so affected is large.

**Non-adherence:** In some circumstances, patients may receive standard care instead of the CSPs intervention when randomized to CSPs. Non-adherence is most likely to occur in the case of the patient who requires urgent neurosurgical intervention and despite CSPs being available, are not used. In keeping with the intention-to-treat analytic design, these patients will be analyzed with the group to which they were randomized.

**Interim Analyses:** The primary safety outcome will be 24-hour mortality. The analyses described earlier will be carried out twice, once when half of the sample has completed the assessment of the endpoint and once when the complete sample has completed the assessment of the endpoint. To control for overall type I error a Bonferroni correction will be employed, allocating 0.025 of the type I error to each analysis.

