Hypothesis for clinical outcomes: Early infusion of cold stored platelets as compared to standard platelet transfusion will result in improved 6 month Extended Glasgow Outcome Scale (GOS-E), lower 24 hour and in-hospital mortality, a lower need for craniotomy/craniectomy, lower need for ICP monitoring, a lower rate of TBI progression, improved hemostatic function, reversal of platelet inhibition and a similar rate of allergic/transfusion reactions and incidence of transfusion related acute lung injury in patients with TBI requiring platelet transfusion.

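### The GOS-E ordinal model takes its covariates from observed imbalance, while baseline GCS is fixed for the other outcomes; fixing GCS here too, and naming the main GOS-E analysis, is a cheap minor improvement

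*Combined protocol and SAP*

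**What the plan says.** All references are to the combined protocol and SAP.

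- **Two GOS-E analyses.** GOS-E is the principal secondary clinical outcome and has 8 ordered levels. Under Analysis for Clinical Outcomes: "A two-sided Chi-square test will be used to compare the distribution of the GOS-E between the treatment arms". Next: "An ordinal polytomous regression model will then be used to assess the independent impact of CSP on GOS-E". The rule for that model's covariates is worded as follows: "after controlling for potential confounding effects of baseline characteristics which reveal imbalance between treatment groups". No candidate list and no definition of imbalance are given.
- **Other outcomes.** The binary outcomes get a logistic model for the effect of CSP "on the secondary trial outcomes while adjusting for baseline GCS". The Cox and analysis-of-covariance models in the same section also fix baseline GCS.
- **Signs that the chi-square leads.** The alternative hypothesis is unordered: "There is a difference in the distribution of the GOS-E scores by treatment group". The chi-square is listed first. The only GOS-E power statement (Sample Size Justification and Power Analysis) is for the 2x8 table with 7 degrees of freedom: 80% power at effect size 0.3788, alpha 0.05, 50 per arm. No sentence names either analysis as main.
- **Alpha.** Interim Analyses names 24-hour mortality as the primary safety outcome, then gives 0.025 to each of two runs of the analyses described before it. Whether that covers GOS-E is not said.

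**The concern.** The principal clinical outcome has the least specified model in the section. Under randomisation, how prognostic a variable is has no bearing on whether it happens to be imbalanced. An imbalance rule therefore often leaves out the variable worth adjusting for, and the model cannot be written down before the data are seen. GCS is already recorded and is the plan's own standard covariate elsewhere.

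The implied lead test also ignores the order of the categories and gives no effect estimate or direction, although the clinical hypothesis is that GOS-E improves. Aim 1 is to find the population and primary outcome for a larger multicenter trial. An odds ratio with an interval from a model fixed in advance serves that aim better than a 7-df p-value.

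**Working it through.** **1. The plan's own figure.** Noncentral chi-square with 7 df: noncentrality = N × w² = 100 × 0.3788² = 14.35. At alpha 0.05, power is 79.99%, so the stated 80% reproduces. At alpha 0.025 it would be 71%.

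**2. How often GCS enters the model.** The plan gives no imbalance rule, so two kinds are assumed.
- *p-value rule.* Under randomisation, GCS passes about as often as the threshold. Simulated entry was 5-6%, 9-11% and 19-21% at p<0.05, 0.10 and 0.20.
- *Standardised-difference rule.* With 50 per arm the standard error is √(2/50) = 0.2. A cut of 0.1 gives P(|Z| > 0.5) = 62%; a cut of 0.2 gives P(|Z| > 1) = 32%.

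**3. Effect on power of the ordinal model.** The documents give no GOS-E distribution or GCS effect. Assumed: control percentages for levels 1 to 8 of 25/2/13/12/12/12/12/12 (distribution B), latent logistic model, conditional odds ratio 2.5, 50 per arm, alpha 0.05. Simulated figures carry an error of a point or two.

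| GCS effect (log-odds per SD) | p<0.05 rule | Std. difference > 0.1 | GCS always in |
|---|---|---|---|
| 0.5 | 72% | 73% | 74% |
| 1.0 | 59% | 66% | 71% |

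Fixing GCS gains 74 − 72 = 2 to 71 − 59 = 12 points over the p<0.05 rule. At the stronger effect, the standardised-difference rule keeps (66 − 59)/(71 − 59) = 7/12, about 60% of the gain. At a weak effect of 0.2, fixing GCS adds about 1 point over no adjustment (73.5% to 74.8%).

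A separate simulation (GCS effect 1.2, a second prognostic covariate, 8 candidates, p<0.05 rule, conditional odds ratio 2.75) gave 59% unadjusted, 58% by imbalance and 73% with GCS fixed.

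Type I error across the settings in which it was checked was about 3.4-5.1% for imbalance-chosen covariates and 4.1-5.4% with GCS fixed.

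**4. Chi-square against an ordinal test.** 50 per arm, alpha 0.05, Wilcoxon standing in for the unadjusted ordinal model. Besides B, four other control distributions were assumed: A 30/3/15/12/12/10/10/8, C 12/1/10/8/12/15/20/22, D 12.5 each, E 8/1/6/6/9/15/25/30. The first three rows are ranges over all five; the last three use B.

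| Pattern of benefit | Chi-square | Ordinal |
|---|---|---|
| Proportional shift, OR 2.0 | 21-23% | 48-50% |
| Proportional shift, OR 2.5 | 36-40% | 70-74% |
| Proportional shift, OR 3.0 | 53-57% | 85-88% |
| 15 / 20 points moved from death to levels 3-5 | 27 / 57% | 14 / 22% |
| 15 / 20 points moved from death to levels 3-8 | 24 / 50% | 27 / 44% |
| 15 / 20 points moved from death to levels 7-8 | 30 / 61% | 51 / 76% |

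The ranking depends on where the benefit falls.

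**5. Detectable effect if the ordinal model leads.** Unadjusted Whitehead formula: V = (N/12)(1 − Σp̄³), log OR = (1.960 + 0.842)/√V. For distribution D, using control proportions alone, Σp³ = 8 × 0.125³ = 0.0156, V = 8.33 × 0.9844 = 8.20, log OR = 2.802/2.864 = 0.978 and OR = 2.66. With p̄ averaged over both arms it is 2.67. Over A to E the range is 2.67-2.77 (2.94-3.08 at alpha 0.025). The GCS-adjusted model at a conditional odds ratio of 2.7 gave 78-81% power in B and 74-76% in E.

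**The case against.** The strongest reply is that nothing here is wrong. The chi-square is valid, matches the hypotheses as worded, and has the power claimed. An ordinal estimate will be produced anyway. An unadjusted test followed by an adjusted model is the plan's pattern for every outcome type. Feasibility is primary, and no decision rule uses the GOS-E p-value. All of that stands and keeps the point minor.

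Three stronger readings are tempting, and the documents do not support them:
- *That precedence is wholly open.* It is unstated, but the hypotheses, the order of listing and the power statement all point to the chi-square.
- *That the imbalance rule always throws away most of the gain from GCS.* That needs a strict p-value rule, and the plan states none. The baseline significance tests planned at the start of the Statistical Analysis Plan make one plausible but are not linked to this model. Patients with GCS 15 can also be enrolled, so a ceiling could weaken the GCS effect and shrink the gain.
- *That the ordinal model must lead.* The plan gives no effect pattern. It also hypothesises "lower 24 hour and in-hospital mortality", so deaths averted into lower levels is not a remote case, and there the chi-square is the more sensitive test.

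What survives is the inconsistency within one section: an open covariate rule for GOS-E beside a fixed one for everything else, with no stated main analysis or alpha.

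**Conclusion.** The point holds as a minor, near-free improvement. Replacing the imbalance rule with fixed GCS makes the model known in advance and is worth about 2 to 12 points of power against a p<0.05 rule, less against a looser rule, and about 1 point if GCS is only weakly prognostic. These sizes rest on an assumed GOS-E distribution, odds ratio and GCS effect. A reader might infer that selection by imbalance inflates false positives; the simulations, with the rule applied mechanically, show no such inflation. The cost of the present rule is lost precision and analyst latitude. The choice of lead test is a separate matter that the sponsor should settle explicitly.

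**What to change.** In Analysis for Clinical Outcomes:

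1. Replace the imbalance rule with baseline GCS as the fixed covariate of the GOS-E ordinal model. Define it as presenting GCS (Severity Stratification), since Data Management also lists a lowest prehospital value and an in-hospital one.
2. Report the common odds ratio with 95% CI, and the odds ratio at each GOS-E cut point as a check of proportional odds.
3. Name the main GOS-E analysis and its alpha: 0.05 as in the power statement, or 0.025 if the interim split is meant to apply.
4. Making the ordinal model main is recommended if a general shift along the scale is expected, but it is the sponsor's choice. If so, keep the 2x8 chi-square and death versus alive by arm as supportive, and add a power statement for the model actually used, with its assumed control distribution. The unadjusted odds ratio of 2.67-2.77 should not be quoted as the 80% point of the adjusted model.

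Cost: SAP wording and one covariate degree of freedom; no new data or patients. If the ordinal model leads, sensitivity to the deaths-averted pattern falls. A 6-month death-versus-alive comparison partly covers this: for 15 / 20 points of deaths averted its power is 54 / 85% in distribution B and 44 / 74% in A. The planned 24-hour and in-hospital mortality outcomes see only deaths within those windows.

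### The GCS-adjusted logistic and Cox models give no finite treatment effect when one arm has no events, and no sparse-event method is specified for 24-hour mortality or the other rare outcomes

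*Combined protocol and SAP*

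**What the plan says.** Under Analysis for Clinical Outcomes, binary outcomes are first compared without adjustment: "For binary outcomes, a two-sided Chi-square test for proportions will be used to compare the proportions". The adjusted model follows: "A logistics regression model will then be used to assess the independent impact of CSP on the secondary trial outcomes while adjusting for baseline GCS". Time to death is handled in parallel. After Kaplan-Meier curves, "a log-rank test will be used to compare the distribution of the cumulative proportion", and then "A Cox-proportional hazards regression model will be used to assess the independent impact of CSP on time to death after controlling for baseline GCS".

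Under Interim Analyses, "The primary safety outcome will be 24-hour mortality", and "The analyses described earlier will be carried out twice, once when half of the sample has completed the assessment of the endpoint"; the second run is at full sample. The multiplicity rule is Bonferroni, "allocating 0.025 of the type I error to each analysis".

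The Outcomes section also lists transfusion reactions, TRALI and thromboembolic events as secondary outcomes. These are binary and so go through the same logistic model.

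The plan does not give an expected rate for any of these events, a method for sparse or empty cells, a choice between Wald and likelihood-ratio inference, or a rule on whether the unadjusted or adjusted result decides the 24-hour mortality comparison.

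**The concern.** Logistic and Cox regression, as ordinarily fitted by maximum likelihood, need events in both arms to estimate a treatment effect. With deaths in only one arm the likelihood keeps rising as the treatment coefficient grows, so there is no maximum. Software stops at an arbitrary large coefficient with a far larger standard error.

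The setting makes this a practical matter. The first look has about 25 patients per arm. Patients hypotensive in the ED are excluded and patients with GCS 15 can be enrolled, so low 24-hour mortality is plausible. TRALI and transfusion reactions could be rarer still.

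At stake is what the DSMB reads at a look. It could hold two planned results for the same outcome, one below the threshold and one near 1, with no effect estimate from the adjusted model and no rule for choosing between them. Settling the matter after seeing the data is what pre-specification is meant to prevent.

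**Working it through.** **Inputs from the document.** 50 per arm (Sample Size Justification); 1:1 allocation (Randomization and Masking), hence about 25 per arm at half sample; 0.025 per look (Interim Analyses). **Assumed:** event rates of 1% to 10%, because none are stated, and a GCS distribution for the adjusted fits.

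**The plan's own figures.** The only power figure is for GOSE: w = 0.3788, 7 df, N = 100. Noncentrality is 100 × 0.3788² = 14.35, giving power 0.80 as stated. The error split is 2 × 0.025 = 0.05. Nothing is computed for 24-hour mortality.

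**Step 1: how often exactly one arm is empty.** With rate p in both arms and q = (1 − p)^n, the probability is 2q(1 − q). Both arms are empty with probability q².

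| n per arm | p | q | exactly one empty | both empty |
|---|---|---|---|---|
| 25 | 2% | 0.603 | 48% | 36% |
| 25 | 5% | 0.277 | 40% | 8% |
| 25 | 10% | 0.072 | 13% | 0.5% |
| 50 | 1% | 0.605 | 48% | 37% |
| 50 | 2% | 0.364 | 46% | 13% |
| 50 | 5% | 0.077 | 14% | 0.6% |
| 50 | 10% | 0.005 | 1% | <0.1% |

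For the Cox model, p is the probability of death over whatever follow-up is analysed. If that runs past 24 hours, p is larger and an empty arm less likely.

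**Step 2: one interim example, 5/25 vs 0/25.**

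- Pearson chi-square: 50 × (5×25 − 0×20)² / (25×25×5×45) = 5.56, p = 0.018. Expected deaths are 2.5 per arm. Fisher's exact p is 0.050 and the continuity-corrected p is 0.059.
- Unadjusted Wald: the variance of the log odds ratio is 1/5 + 1/20 + 1/0 + 1/25, which is not finite. With GCS in the model, the fitted Wald p is about 0.999.
- Unadjusted likelihood ratio: 2 × [(5 ln 0.2 + 20 ln 0.8) − (5 ln 0.1 + 45 ln 0.9)] = 2 × (−12.51 + 16.25) = 7.49, p = 0.006. With GCS in the model, p is about 0.004 to 0.006. The odds ratio remains infinite.
- Firth: without covariates it equals adding 0.5 to each cell, so the odds ratio is (5.5 × 25.5)/(20.5 × 0.5) = 13.7. With GCS in the model, the odds ratio is about 13 to 17 and the penalised likelihood-ratio p about 0.016 to 0.022, depending on the GCS distribution assumed.

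**Step 3: full sample, GCS-adjusted.** For 6/50 vs 0/50:

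- logistic: coefficient about 24, SE about 67,000, Wald p 1.00
- Cox: coefficient about 28, SE above 10^5, Wald p 1.00
- likelihood ratio: p about 0.003 in both models
- chi-square 0.0115, Fisher 0.027
- Firth logistic: odds ratio about 14, p about 0.012

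**Step 4: where the models work.** With deaths in both arms there is no breakdown. For 8/50 vs 1/50, Wald p is 0.038 and chi-square 0.014. For 16/50 vs 4/50, they are 0.005 and 0.003.

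**The case against.** The case on the other side has several sound parts.

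- **Wald is not specified.** The plan names the models, not the test. A likelihood-ratio test from the same fit preserves the signal, so a p-value near 1 is a property of common default output, not of the written plan. This stands. The likelihood-ratio test still leaves no finite odds or hazard ratio, though, and the choice of test remains open.
- **The signal is not lost.** The unadjusted chi-square and log-rank come first at both looks, and the DSMB also reviews adverse events and can meet urgently. Nothing makes the adjusted p-value decisive. This stands too. What remains is two conflicting planned results with no order between them.
- **The failure is not specific to harm.** A reader might infer that the adjusted result is worst exactly when harm is clearest. The documents do not support that. The trigger is an empty arm: it occurs equally at 1 vs 0 and when the cold-stored platelet arm is the one without deaths. Clear harm with deaths in both arms is handled adequately.
- **The frequency is easily overstated.** A reader might count every trial with at least one empty arm, which at 25 per arm and 2% gives 84%. Of that, 36 points are trials with no events at all, where no result exists to conflict. A split as extreme as 0 vs 5 or more of 25 is rare under equal rates: 0.01% at 2%, 0.4% at 5% and 1.4% at 10%. With true rates of 2% vs 10%, control 0 and CSP at least 5 has a probability of about 6%.
- **The example is borderline.** Fisher's 0.050 does not reach 0.025.

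**Conclusion.** The point holds as a limited but real defect. When exactly one arm has no events, the planned adjusted models cannot supply a finite treatment effect, and their Wald interval and p-value are meaningless. At the half-sample look this pattern has a chance of 40% to 48% if the event rate is 2% to 5%, and 13% at 10%. At full sample it ranges from 48% at 1% to 1% at 10%. These figures rest on equal assumed rates in the two arms, since the documents give none. If 24-hour mortality is 10% or more, the problem is small by the final analysis, although the rarer safety outcomes may still meet it.

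The evidence does not show that the plan would hide harm or that the DSMB would be left without a usable test. A sharp conflict between the planned results is much less common than an empty arm. The primary feasibility outcome is unaffected. The change is worth making before the first look because it is cheap and concerns the primary safety outcome.

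**What to change.** In Analysis for Clinical Outcomes, name 24-hour mortality, TRALI, transfusion reactions, thromboembolic events and time to death as potentially sparse. For these, fit the GCS-adjusted models as Firth penalised-likelihood logistic and Cox regression, with profile penalised-likelihood confidence intervals and tests. Under Interim Analyses, apply them at both looks.

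Beside each adjusted binary result, report the unadjusted risk difference with a score-based 95% confidence interval, which stays interpretable with an empty arm. State in advance which result governs the 24-hour mortality comparison. Outcomes that are not sparse can keep the models as written.

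The cost is a few lines of SAP text and slight shrinkage of the estimates. Firth options are standard in statistical software, and where events are plentiful the results barely change.
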